### 17.3. ADVERSE DEVICE EFFECTS (ADE)

An adverse device effect is defined as any untoward adverse event related to the use of an investigational or unintended response to a medical device.

Note 1: This definition includes adverse events resulting from insufficient or inadequate Instructions for Use, deployment, implantation, installation, or operation, or any malfunction of

the investigational medical device. This definition includes any event resulting from insufficiencies or inadequacies in the Instructions for Use or the deployment of the device or any event that is a result of not observing the IFU (See **Section 18**).

Note 2: This definition includes any event resulting from use error or from intentional misuse of the investigational medical device (See **Section 18**).

A list of events that may be associated with the study device and/or the study device procedure is provided in **Section 16.1**.

#### 17.3.1. ADE REPORTING

All ADEs must be evaluated to determine whether the event further meets criteria for an SADE (See **Section 17.6**) and would be subject to respective reporting requirements. Non-serious, anticipated ADEs must be reported by the Investigator (or designee) to the Sponsor in a timely manner and must also be submitted to the IRB/EC per policy. If the event occurred as a result of a device event, respective reporting requirements must be followed as outlined in **Section 18**.

#### 17.4. SERIOUS ADVERSE EVENTS (SAE)

A serious adverse event (SAE) is defined an adverse event that:

- led to death,
- led to a serious deterioration in the health of the subject, that either resulted in:
  - a life-threatening illness or injury, or
  - resulted in a permanent impairment of a body structure or a body function, or
  - required in-patient hospitalization or prolongation of existing hospitalization, or
  - resulted in medical or surgical intervention to prevent life-threatening illness or injury or permanent impairment to body structure or a body function, or,
- led to fetal distress, fetal death or a congenital abnormality or birth defect.

Note: Planned hospitalization for a pre-existing condition, or a procedure required by the investigational plan without serious deterioration in health, is not considered a serious adverse event.

#### 17.4.1. SAE REPORTING

All SAEs must be evaluated to determine whether the event further meets criteria for an SADE (See **Section 17.6**) and would be subject to respective reporting requirements. All events that meet the criteria above for SAEs must be reported by the Investigator (or designee) to the Sponsor **within 2 business days from first knowledge of event** and must also be reported to the IRB/EC per the respective policy.

#### 17.5. MAJOR ADVERSE LIMB EVENTS (MALE) + PERIOPERATIVE DEATH (POD)

For the purpose of this study, the definition of major limb adverse event(s)(MALEs)+POD include the following outcomes:

- All-cause death less than 30 days after the Index Procedure
- Above-ankle target limb amputation
- Major re-intervention to the target lesion (defined as new bypass graft, jump/interposition graft revision, or thrombectomy / thrombolysis)

#### 17.5.1. MALE+POD REPORTING

All events that lead to any of the outcomes meeting criteria above for an MALE+POD must be reported by the Investigator (or designee) to the Sponsor **within 2 business days from first knowledge of the event**, and must also be reported to the IRB/EC per the respective policy.

#### 17.6. SERIOUS ADVERSE DEVICE EFFECTS (SADE)

A serious adverse device effect (SADE) is defined as an adverse device effect (ADE) that results in any of the consequences characteristics of a serious adverse event (SAE).

##### 17.6.1. SADE REPORTING

All events that meet the criteria above for an SADE must be reported by the Investigator (or designee) to the Sponsor **within 2 business days from first knowledge of event** and must also be reported to the IRB/EC per policy. If the event occurred as a result of a device event, respective reporting requirements must be followed as outlined in **Section 18**.

#### 17.7. UNANTICIPATED ADVERSE DEVICE EFFECTS (UADE)

Any serious adverse effect on health or safety or any life-threatening problem or death caused by, or associated with, a device, if that effect, problem, or death was not previously identified in nature, severity, or degree of incidence in the investigational plan or application (including a supplementary plan or application), or any other unanticipated serious problem associated with a device that relates to the rights, safety, or welfare of subjects.

##### 17.7.1. UADE REPORTING

Any event that is suspected of meeting UADE criteria should be reported in the same manner as an SAE or SADE and must be reported by the Investigator (or designee) to the Sponsor **within 2 business days from first knowledge of event** and must also be reported to the IRB/EC per the respective policy. All SAEs will be reviewed by the Sponsor (or designee) to determine if UADE criteria is met, and if so, will immediately conduct an evaluation and report the results of the evaluation to FDA, all reviewing IRBs/ECs, and participating investigators within 10 business days after the Sponsor first receives notice of the effect.

## 18. STUDY DEVICE EVENT REPORTING

A Study Device Event refers to the performance of the study device and the occurrence of a deficiency or malfunction as defined in sub-sections below. Device events are to be reported on the Device Event eCRF and submitted to the sponsor as soon as possible and **within 2 business days of first knowledge of occurrence**. Any adverse event suspected of resulting from a device event must be reported per the required timelines as outlined in **Section 17**.

### 18.1. DEVICE DEFICIENCY

Inadequacy of a medical device related to its identity, quality, durability, reliability, safety or performance, such as malfunction, misuse or not observing the IFU, and inadequate labeling.

### 18.2. DEVICE MALFUNCTION

A malfunction is defined as a failure of a device to meet its performance specifications or otherwise to perform as intended

### 18.3. DEVICE RETURNS

In the event that a device is suspected of deficiency or malfunction, the Investigator should make every effort to return the device to the manufacturer, Intact Vascular. The Investigator or designee shall contact Intact Vascular for a return manufacturer authorization (RMA) number and for additional instructions for the return of potentially biohazardous material.

## 19. STATISTICAL METHODS AND CONSIDERATIONS

### 19.1. STUDY DESIGN

This is a prospective, multi-center, single-arm, non-blinded study designed to investigate the safety and efficacy of the Tack Endovascular System.

### 19.2. ANALYSIS POPULATIONS

Subjects with BTK PAD who receive PTA in the Mid/Distal Popliteal, Tibial, and Peroneal Arteries and have a resulting dissection(s) that an Investigator would otherwise treat by means such as additional angioplasty with extended inflation time or stenting, are eligible for enrollment. To be enrolled, subjects must meet all inclusion criteria and not meet any of the exclusion criteria

The intent to treat (ITT) population will consist of all subjects who had the Tack Endovascular System advanced through the introducer sheath. ITT subjects are included in both primary and secondary endpoint analyses.

The PP population will be the subset of the ITT population that have met the definition of device success and have not had any major protocol deviations. Major protocol deviations include:

- A major inclusion/exclusion criterion violation; or
- A major procedural deviation

The criteria for deviations meeting the classification of “major” will be defined by an independent designee before study endpoint data is available for statistical analysis.

### 19.3. PRIMARY ENDPOINTS

#### 19.3.1. SAFETY

Freedom from major adverse limb events (MALE) plus peri-operative death (POD) at 30 days defined as a composite of all-cause death, above-ankle target limb amputation, or major re-intervention to the target lesion(s) (defined as new bypass graft, jump/interposition graft revision, or thrombectomy / thrombolysis)

### 19.3.2. EFFICACY

The primary efficacy endpoint is freedom from MALE at 6 months + POD at 30 days.

### 19.4. SECONDARY ENDPOINTS

- Target lesion(s) tacked segment(s) patency at 6 months defined as the presence of blood flow using duplex ultrasound. If angiography is available within the 6-month follow-up visit window, it should be used in place of the duplex ultrasound. Evidence of no blood flow within the Tacked segment indicates restenosis/loss of patency.
- Target Limb Salvage defined as freedom from any above-ankle target limb amputation at 6 months.

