Primary Endpoints:	
Safety: Freedom from major adverse limb events (MALE) plus perioperative death (POD) at 30 days defined as a composite of all-cause death, above-ankle target limb amputation, or major re-intervention to the target lesion(s) (defined as new bypass graft, jump/interposition graft revision, or thrombectomy / thrombolysis)
 
Efficacy: Freedom from MALE at 6 months + POD at 30 days

Secondary Efficacy Endpoints:	
 
▪ Target lesion(s) tacked segment(s) patency at 6 months defined as the presence of blood flow using duplex ultrasound. If angiography is available within the 6-month follow-up visit window, it should be used in place of the duplex ultrasound. Evidence of no blood flow within the Tacked segment indicates restenosis/loss of patency.
 
▪ Target Limb Salvage defined as freedom from any above-ankle target limb amputation at 6 months.
 

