### 6.3. OBSERVATIONAL ENDPOINTS

- Device Success: Successful deployment of the Tack implant(s) at the intended target site(s) and successful withdrawal of the delivery catheter from the introducer sheath.
- Target Lesion Success: Demonstrated target lesion patency [ $<30\%$  residual diameter stenosis (DS), by visual estimate] without the use of a bailout stent within the target lesion upon completion of the index procedure. This will be assessed for all lesions treated with a Tack implant. In addition, target lesion success will also be analyzed by lack of bailout stent to tacked segment only. Multiple target lesions treated as one lesion with PTA will be analyzed as one lesion.
- Procedural Success: Demonstrated target lesion patency ( $<30\%$  residual DS, by visual estimate) without the use of a bailout stent within the target lesion and without the occurrence of MALE+POD upon completion of the index procedure
- Amputation-free survival (AFS): Freedom from above-ankle target limb amputation or all-cause death at 6 and 12 months
- Freedom from MALE at 12 months + POD at 30 days
- Target lesion(s) tacked segment(s) patency at 12 months defined as the presence of blood flow using duplex ultrasound.
- Target Limb Salvage defined as freedom from any above-ankle target limb amputation at 12 months
- Assisted primary target lesion Tacked segment patency (flow vs. no flow) at 6 and 12 months
- Secondary target lesion Tacked segment patency (flow vs. no flow) at 6 and 12 months
- PSVR patency at 6 and 12 months [Freedom from binary restenosis defined as Peak Systolic Velocity Ratio (PSVR) of  $\geq 2.5$  and/or angiographic percent diameter stenosis of  $\geq 50\%$ ] assessed for the following:
  - Target Lesion(s), defined as the entire contiguous arterial segment treated with angioplasty, inclusive of an additional proximal and distal margin of 5 mm

- Tacked Segment(s), defined as the Tack device and 5 mm of artery proximal and distal to each Tack. If Tacks are within 10 mm of each other, they will be considered as a single tacked segment for the purposes of this patency assessment.
- Clinically-driven target lesion revascularization (CD-TLR) through 12 months
- Clinically-driven target vessel revascularization (CD-TVR) through 12 months
- All-cause death through 12 months
- Any Target vessel revascularization (TVR) through 12 months
- Any Target lesion revascularization (TLR) through 12 months

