### 19.5. OBSERVATIONAL ENDPOINTS

- Device Success: Successful deployment of the Tack implant(s) at the intended target site(s) and successful withdrawal of the delivery catheter from the introducer sheath.
- Target Lesion Success: Demonstrated target lesion patency [ $<30\%$  residual diameter stenosis (DS), by visual estimate] without the use of a bailout stent within the target lesion upon completion of the index procedure. This will be assessed for all lesions treated with a Tack implant. In addition, target lesion success will also be analyzed by lack of bailout stent to tacked segment only. Multiple target lesions treated as one lesion with PTA will be analyzed as one lesion.
- Procedural Success: Demonstrated target lesion patency ( $<30\%$  residual DS, by visual estimate) without the use of a bailout stent within the target lesion and without the occurrence of MALE+POD upon completion of the index procedure
- Amputation-free survival (AFS): Freedom from above-ankle target limb amputation or all-cause death at 6 and 12 months
- Freedom from MALE at 12 months + POD at 30 days
- Target lesion(s) tacked segment(s) patency at 12 months defined as the presence of blood flow using duplex ultrasound.
- Target Limb Salvage defined as freedom from any above-ankle target limb amputation at 12 months
- Assisted primary target lesion Tacked segment patency (flow vs. no flow) at 6 and 12 months
- Secondary target lesion Tacked segment patency (flow vs. no flow) at 6 and 12 months
- PSVR patency at 6 and 12 months [Freedom from binary restenosis defined as Peak Systolic Velocity Ratio (PSVR) of  $\geq 2.5$  and/or angiographic percent diameter stenosis of  $\geq 50\%$ ] assessed for the following:
  - Target Lesion(s), defined as the entire contiguous arterial segment treated with angioplasty, inclusive of an additional proximal and distal margin of 5 mm
  - Tacked Segment(s), defined as the Tack device and 5 mm of artery proximal and distal to each Tack. If Tacks are within 10 mm of each other, they will be considered as a single tacked segment for the purposes of this patency assessment.
- Clinically-driven target lesion revascularization (CD-TLR) through 6 and 12 months
- Clinically-driven target vessel revascularization (CD-TVR) through 6 and 12 months

- All-cause death through 6 and 12 months
- Any Target vessel revascularization (TVR) through 6 and 12 months
- Any Target lesion revascularization (TLR) through 6 and 12 months

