and a one-sided Type I error rate of 2.5%, a sample size of 171 subjects provides 90% power to demonstrate that the observed 30-day MALE+POD rate is below the performance goal of 12%.

Since the required sample size for the primary efficacy endpoint (186), is larger than the required sample size for the primary safety endpoint (171), an effective sample size of 186 subjects meeting the ITT definition will be assumed. Assuming approximately 20% loss to follow-up, total enrollment will be  $186/0.80$  or 232 subjects.

The secondary endpoint of primary patency of the tacked segment of the treated lesion at 6 months will also be formally tested against a performance goal of 64%. The performance goal of 64% was chosen as a result of a meta-analysis combining 13 papers that reported 6-month patency for standard PTA or from which the 6-month patency rate could be derived. These papers covered several patient populations, however all these populations are target populations for use of the Tack. A meta-analysis was performed on the results reported in these papers and the random effects estimate of 6-month patency was 63.5%. Therefore, 64% was chosen as the performance goal. Assuming an observed 6-month patency rate of 81% and a one-sided Type I error rate of 2.5%, the effective sample size given above for the primary efficacy endpoint of 175 would provide greater than 90% power to detect the difference between an observed 6-month patency of 81% and the performance goal of 64%.

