### 19.8.3. SECONDARY EFFICACY ENDPOINTS

The secondary efficacy endpoint of 6-month patency will be estimated as the proportion of tacked segments of the lesion(s) that are still patent at 6 months. A one-sided lower 97.5% confidence bound will be calculated for this estimate using the standard normal approximation. This lower bound will be compared to the performance goal of 64%. The hypotheses being tested are:

$$H_0 : P_{\text{Patency}_{6\text{month}}} \leq 64\%$$

$$H_a : P_{\text{Patency}_{6\text{month}}} > 64\%$$

where  $P_{\text{Patency}_{6\text{month}}}$  is the proportion of subjects whose tacked portion of the vessel is still patent 6 months post procedure. Patency will also be displayed using a Kaplan-Meier curve.

The secondary efficacy endpoint of target limb salvage at 6 months will be summarized using the Kaplan-Meier method to estimate freedom from above-ankle target limb amputation. The final 6-month estimate will be presented along with 95% confidence intervals. All subjects that meet the ITT definition are included in this analysis.

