Assisted Primary Target Lesion Tacked Segment Patency	Assisted primary patency (freedom from total occlusion) achieved with the use of an additional or secondary surgical or endovascular procedures, as long as total occlusion of the Tacked segment has not occurred prior to such procedures. In all cases, freedom from total occlusion is confirmed by angiography or DUS (flow vs. no flow) if angiography was not performed.

Term	Definition
Bailout Stenting	Unplanned stenting to the target lesion and/or Tack implant(s). The use of a bailout stent may occur in the event of persistent flow-limiting dissection not able to be treated with the Tack (or as otherwise required for safety of the subject).
Balloon Angioplasty	A catheter containing an inflatable balloon (standard uncoated) is advanced through a narrowed or occluded portion of an artery and inflated in order to open the artery and restore blood flow. Also referred to as “PTA” (percutaneous transluminal angioplasty).
Binary Restenosis	Greater than or equal to 50% restenosis determined by angiography or by duplex ultrasound derived peak systolic velocity ratio (PSVR) of $\geq 2.5:1$ .
De Novo Lesion	A lesion in the artery that has not been previously treated.
Device Deficiency	Inadequacy of a medical device related to its identity, quality, durability, reliability, safety or performance, such as malfunction, misuse or not observing the IFU and inadequate labeling.
Device Malfunction	A malfunction of a device to perform in accordance with its intended purpose when used in accordance with the Instructions for Use.
Device Success	Successful deployment of the Tack(s) at the intended target site(s) and successful withdrawal of the delivery catheter from the introducer sheath.
Dissection	Disruption of an arterial wall resulting in separation of the intimal layer. May or may not be flow limiting.
	Dissection Types (National Heart, Lung and Blood Institute – NHLBI)
Type A	Small radiolucent area within the lumen of the vessel disappearing with the passage of the contrast material.
Type B	Appearance of contrast medium parallel to the lumen of the vessel disappearing within a few cardiac cycles.
Type C	Dissection protruding outside the lumen of the vessel persisting after passage of the contrast material.
Type D	Spiral shaped filling defect with or without delayed run-off of the contrast material in the antegrade flow.

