Minor Re-intervention	Endovascular procedures (PTA, atherectomy, stenting) without thrombectomy/thrombolysis, and minor surgical revisions (patch angioplasty) occurring after the index procedure
Myocardial Infarction (MI)	Q wave MI (QWMI): requires one of the following criteria:
	
 
• Chest pain or other acute symptoms consistent with myocardial ischemia and new pathological Q waves in two or more contiguous ECG leads
 
• New pathologic Q waves in two or more contiguous ECG leads and elevation of cardiac enzymes above normal.
 

	Non-Q Wave MI (NQWMI): defined as either: elevated CK = 2X the laboratory upper limit of normal with the presence of an elevated CK-MB (any amount above the laboratory upper limit of normal) in the absence of new pathological Q waves or elevated CK-MB = 3X the laboratory upper limit of normal in the absence of new pathological Q waves.

Term	Definition
Peak Systolic Velocity Ratio (PSVR)	A measurement (using Duplex Ultrasonography) of peak velocity of blood (cm/sec) within a lesion or stented vessel segment that is divided by the peak velocity of blood (cm/sec) proximal to the lesion of stented segment.
Per-protocol (PP) subjects	
The per-protocol (PP) population is defined as ITT subjects with evaluable data that have met the definition for device success, excluding subjects with major protocol deviations such as:
 
 
▪ A major inclusion/exclusion criterion violation; or
 
▪ A major procedural deviation
 
 
The criteria for deviations meeting the classification of “major” will be defined by an independent designee before study endpoint data is available for statistical analysis.

Perioperative Death (POD)	All-cause death occurring at 30 days after the Index Procedure
Primary Efficacy Endpoint	Freedom from major adverse limb events (MALE) at 6 months plus peri-operative death (POD) at 30 days defined as a composite of all-cause death, above-ankle target limb amputation, or major re-intervention to the target lesion(s) (defined as new bypass graft, jump/interposition graft revision, or thrombectomy / thrombolysis)

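### The formally tested 6-month patency endpoint, labelled primary patency in 19.6, is defined by flow alone and has no rule for a tacked segment re-treated while still flowing

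*Combined protocol and SAP*

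**What the plan says.** Section 19.4 defines the endpoint as "Target lesion(s) tacked segment(s) patency at 6 months defined as the presence of blood flow using duplex ultrasound", with angiography replacing duplex if it is available in the visit window. The same definition stands in the synopsis, 6.2 and Section 24. The only failure rule, as worded in the synopsis, is "Evidence of no blood flow within the Tacked segment indicates restenosis/loss of patency".

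Section 19.6 gives the endpoint a narrower name: "The secondary endpoint of primary patency of the tacked segment of the treated lesion at 6 months will also be formally tested", against a goal of 64% with an assumed rate of 81%. Section 19.8.3 compares a one-sided 97.5% lower bound, by the normal approximation, with 64%. The tested quantity there "is the proportion of subjects whose tacked portion of the vessel is still patent 6 months post procedure". A Kaplan-Meier display is added without an event definition. Under 19.13, patency is tested only after both primary endpoints are met, and limb salvage carries no hypothesis.

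The observational list in 19.5 includes "Assisted primary target lesion Tacked segment patency (flow vs. no flow) at 6 and 12 months". Section 24 defines assisted primary patency as freedom from total occlusion achieved with further procedures, "as long as total occlusion of the Tacked segment has not occurred prior to such procedures". Secondary patency is a further separate endpoint.

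**The concern.** The plan separates primary, assisted primary and secondary patency by name, but the definition of the tested endpoint does not carry the separation. A tacked segment that is stenosed but open, is re-treated, and flows on the 6-month scan meets the written definition of success. It also meets the Section 24 description of assisted primary patency. For such segments the two endpoints cannot be told apart.

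No other tested endpoint picks this up. MALE covers above-ankle amputation and major re-intervention. Section 24 classes as minor "Endovascular procedures (PTA, atherectomy, stenting) without thrombectomy/thrombolysis, and minor surgical revisions (patch angioplasty) occurring after the index procedure". A repeat angioplasty or a stent in the tacked segment therefore does not fail the primary efficacy endpoint. It appears only in the descriptive revascularization endpoints (TLR, TVR and their clinically driven forms).

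At stake is the meaning of the one formal secondary claim: that the tacked segment stayed open unaided, or only that it was open when scanned.

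**Working it through.** **1. The plan's own figure.** Inputs from 19.6: goal 0.64, assumed rate 0.81, one-sided alpha 0.025, n = 175. The same section also gives the effective sample size as 186, so both are run.

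Power = Φ{[(0.81 − 0.64) − 1.96·√(0.64·0.36/n)] / √(0.81·0.19/n)}

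- n = 175: Φ{(0.17 − 1.96·0.03628)/0.02966} = 99.96%.
- n = 186: Φ{(0.17 − 1.96·0.03520)/0.02876} = 99.98%.

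The stated power of more than 90% is reproduced. The point does not depend on it.

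**2. The pass rule in 19.8.3.** Pass if p̂ − 1.96·√(p̂(1 − p̂)/n) > 0.64.

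- n = 186: 132 patent (71.0%) gives a bound of 0.6444 and passes; 131 gives 0.6387 and fails.
- n = 175: 124 patent (70.9%) gives 0.6412 and passes; 123 gives 0.6351 and fails.

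**3. Direction.** Segments that flow at 6 months without re-intervention are a subset of all segments that flow at 6 months. The flow-only rate is therefore the unassisted rate plus r, where r is the share re-treated while flowing and flowing at 6 months. It cannot be lower than the unassisted rate.

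**4. Illustration at the goal.** Assume that 64% means unassisted patency, that the true unassisted rate is exactly 64%, and that there is one unit per subject. The values of r are assumed. The pass probability is the exact binomial chance of reaching the threshold at rate 0.64 + r.

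| r | Measured rate | n = 186 | n = 175 |
|---|---|---|---|
| 0 | 64% | 2.7% | 3.4% |
| 1% | 65% | 5.0% | 6.0% |
| 2% | 66% | 8.7% | 10.0% |

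The first row differs from 2.5% only because of the normal approximation and the discreteness of the count.

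**5. At the planned rate.** If 81% is an unassisted rate, the pass probability is 99.97% (n = 186) or 99.96% (n = 175) under strict scoring, and higher under flow-only scoring.

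**6. Cost of strict scoring if 81% is a flow-only rate.** The strict rate is 0.81 − r.

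- r = 2%: strict rate 79.0%, power 99.6% at either n.
- r = 6.5%: strict rate 74.5%, power about 88% at either n.

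The 6.5% is 100% − 93.5%, the pilot's 6-month freedom from clinically driven TLR in Table 5. It is a target-lesion rate from a 35-subject study, used here as a high value.

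**The case against.** The strongest reply is that unassisted patency is plainly meant. Section 19.6 says primary patency, 19.8.3 says still patent, and an assisted-primary endpoint would be largely redundant if the tested endpoint already included assisted results. No passage states that re-treated segments are successes. Re-treatment would also be visible. Section 24 evaluates clinically driven TLR for the Tack-treated section as well as per lesion, 19.5 reports any TLR and a PSVR-based patency for tacked segments, and 9.4 asks for imaging before any endovascular re-intervention. The Kaplan-Meier and 19.11 questions are not separate faults: both follow from the same missing rule. All of this stands. It does not supply the rule, and the analysis will follow the written definition.

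A second reply is that ending patency at any re-intervention might be stricter than the literature goal, since the pilot's post-hoc definition counted only clinically driven TLR. That is a fair reason to document what the 64% measures. Within this plan, though, the Section 24 definition of assisted primary patency covers further procedures without limiting them to clinically driven ones, so any such procedure is where the plan itself draws the line.

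A reader might go further and infer that the test is biased in the device's favour. The documents do not support that, because Section 19.6 does not give the patency definitions in the 13 papers. Nor is the source of the 81% stated. The pilot's 80.6% is close, but it rested on audible Doppler, clinically driven TLR and major amputation, and does not settle the matter. A reader might also put the pilot's 6.5% into step 4, which gives about a 48% chance of passing (n = 186). That stacks worst cases: an unassisted rate exactly at the goal, and every re-treated target lesion re-treated in its tacked segment, flowing beforehand and flowing at 6 months.

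**Conclusion.** The point holds as a gap between name and definition in the only hypothesis-tested secondary endpoint. Applied as written, the rule counts a segment re-treated while flowing as patent, and this can only raise the tested rate above unassisted patency. The size depends on how many segments are re-treated while flowing, which the documents do not give. The step 4 figures show sensitivity near the goal under their stated assumptions and are not a forecast. At an unassisted 81% the scoring makes no practical difference to the test. Study success under 19.12 is unaffected, because it rests on the two primary endpoints alone. The change should be made, but it does not threaten the trial's main conclusion.

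**What to change.** In the synopsis, 6.2, 19.4, 19.8.3 and Section 24, state that tacked-segment primary patency is lost at the earlier of a no-flow finding or a re-intervention to the tacked segment. Use that event for the Kaplan-Meier curve and in 19.11, so that a later flow finding is not carried back across a re-treatment. Report the flow-only rate as a sensitivity analysis, and leave assisted primary and secondary patency unchanged. State whether the 64% goal and the 81% assumption use the same definition. Make the edit before endpoint data are analysed.

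The cost is text only. TLR is already collected. The ruler location of each Tack is recorded (13.3.3) and later angiograms are to use the same ruler placement (13.1.1), so a re-intervention can be assigned to a tacked segment. The downside is a somewhat lower reported patency rate. Power falls below the stated 90% only if 81% is a flow-only rate and re-treatment is near the high value in step 6.
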